9.1.1.4. Sight-Threatening Adverse Event

A *sight-threatening AE* is any SAE that places the subject at immediate risk of permanently losing vision in either eye as a direct result of the event. An AE will be counted as a sight-threatening AE if the Clinical Investigator checked an 'Sight-Threatening' option under 'Serious Criteria/Category' question on the SAE eCRF.

9.1.1.5. Events of Special Interest

An *event of special interest* (ESI) is a medical event both anticipated and unanticipated that may have a particular impact on the benefit/risk profile of the study medication. For this study, ESIs are specific to the study eye only and are as follows:

- Clinically significant new or worsening of uveitis, defined as satisfaction of any of the following:
 - Worsening of uveitis in the study eye as indicated by at least a 2-step increase in VH score (i.e., 0 to ≥ 2+, 0.5+ to ≥ 3+, 1+ to ≥ 3+, 1.5+ to ≥ 4+, or 2+ to ≥ 4+) as compared to the baseline (Day 1) VH score or the best achieved VH score postbaseline.
 - Severe deterioration of vision in the study eye due to worsening of uveitis that is indicated by at least doubling of the visual angle (loss of 3 or more lines [≥15 ETDRS letters]) as compared to baseline (Day 1) BCVA.
 - New or worsening retinal or choroidal uveitic lesion(s) in the study eye as compared to baseline (Day 1).
 - New or worsening uveitis otherwise deemed clinically significant by the investigator in the study eye as compared to the baseline (Day 1).
- Endophthalmitis / Sterile Endophthalmitis in the study eye
- Traumatic cataract in the study eye
- Vitreoretinal hemorrhage in the study eye
- Drug depot in visual axis in the study eye
- Retinal detachment in the study eye
- Increased IOP (> 10 mmHg as compared to baseline).
- Cataract (new or worsening from baseline) in the study eye

For regulatory reporting requirement, **pregnancy** and **investigational product administration error** considered to be significant by the investigator are also considered ESIs for this study

9.1.2. Safety Measures

Table 3 lists the safety measures to be evaluated for this study.

Table 3:	Safety Assessments
----------	--------------------

Safety Measures	Note
Slit-lamp biomicroscopy: vitreous, eyelid, conjunctiva, cornea, anterior chamber cells and flare, iris and pupil, ocular motility	The status of each of these biomicroscopy parameters was determined as Normal or Abnormal. For each abnormal record, the parameter was rated as $1 = Mild$, $2 = Moderate$, or $3 = Severe$.
Slit-lamp Biomicroscopy: vitreous cell count	This measure was rated as $0 = 0$ cells, $0.5+=1-10$ cells, $1+=11-20$ cells, $2+=21-30$ cells, $3+=31-100$ cells, $4+=>100$ cells
Slit-lamp Biomicroscopy: anterior chamber cells	This measure was rated as $0 = 0$ cells, $0.5+=1-5$ cells, $1+=6-15$ cells, $2+=16-25$ cells, $3+=26-50$ cells, $4+=>50$ cells
Slit-lamp Biomicroscopy: anterior chamber flare	This measure was rated as $0 = None$, $1 + = Faint$, $2 + = Moderate$, $3 + = Marked$, $4 + = Intense$
Slit-lamp Biomicroscopy: lens and cataract	The lens of an eye was classified as Phakic, Aphakic, or Pseudophakic. For phakic lens with cataract, the severity was rates as $1 = Mild$, $2 = Moderate$, $3 = Severe$. In addition, whether cataract affects grading of degree of inflammation (Yes or No) was also determined.
Intraocular pressure	The IOP, the fluid pressure inside the eye, was recorded in mmHg with one decimal point (e.g., 24.0 mmHg). For this study, the elevated IOP, depending on the level of elevation, might be reported as an AE at Clinical Investigator's discretion.
Indirect ophthalmoscopy: retina vessels, macula, fovea, periphery, optic nerve, cup-to- disc ratio	The status of retina vessels, macula, fovea, periphery, and optic nerve was determined as Normal or Abnormal. The cup-to-disc ratio was recorded with two decimal points (e.g., 0.80)
Best-corrected visual acuity (BCVA)	BCVA measures the acuteness or clearness of best-corrected vision, with a range of [0, 110] in ETDRS letters. An increase in BCVA indicates improvement in the best-corrected vision. A 5-letter difference in visual acuity is equivalent to one Snellen line. A BCVA score of 85 ETDRS letters is equivalent to 20/20 vision, which is considered normal vision.
Central Subfield Thickness (CST)	For each eye, the CST was measured using Optical Coherence Tomography (OCT). OCT was performed using reading center certified photographers, equipment, and standardized protocols.

Safety Measures	Note
Physical examination: Height, weight	The physical exam result was determined as Normal, Abnormal, or No Change. The weight and the height were recorded with one decimal point in inch/cm and lb/kg, respectively. The conversion rules "1 lb = 0.453592 kg" and "1 in = 2.54 cm" will be followed to convert lb to kg and into cm, respectively.
Vital signs: Oral temperature, systolic and diastolic blood pressure, heart rate	The oral temperature was recorded in °F or °C. The conversion rule "°C = $5/9 \times (°F - 32)$ " will be followed to convert °F to °C. The blood pressure (systolic and diastolic) and the heart rate were recorded in mmHg and beats per minute (bpm), respectively.
Laboratory tests: Blood chemistry/hematology, urinalysis	The minimum blood and urine parameters collected in the study are listed in Appendix B. Hematology, chemistry, and urinalysis outcomes were determined by the Clinical Investigator as Normal, Not Clinically Significant Abnormality or Clinically Significant Abnormality based on the
	comprehensive review of the relevant laboratory test results.

 Table 3:
 Safety Assessments (Continued)

The safety-related measures collected in this study include AEs, events of special interest (ESIs), slit-lamp biomicroscopy findings, IOP, best-corrected visual acuity, indirect ophthalmoscopy findings, central subfield thickness, physical exam results, vital signs, and laboratory test results. The Safety population will be used for all summaries.

All the safety-related measures will be summarized descriptively by actual treatment received. Except AEs, the descriptive summary of each ocular safety-related measurement and the change from baseline in that measure will be performed for study eyes and fellow eyes separately.

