^a The double-masked period ends with the pre-dose evaluations at Month 6; the first open-label dose of DE-109 is at Month 6.

^b On study visits during the double-masked period at which IP is administered, the unmasked investigator will perform the IP preparation and administration.

^c Signed and dated informed consent form must be obtained prior to conducting any study-related activities.

^d If physical examination and vital signs, VFQ-25 and/or laboratory safety tests were performed at Month 3 under a previous version of the protocol these assessments do not need to be performed at Month 5.

^e Serum and urine pregnancy tests are to be performed on all females of child-bearing potential. Urine pregnancy test (hCG) is to be performed prior to each IP administration. A positive pregnancy test at screening or Day 1 (Baseline) requires exclusion from the study. At subsequent visits, a positive urine pregnancy test requires immediate discontinuation from the study. Pregnancy is an event of special interest and requires follow-up by Santen until the outcome is known.

^f At Month 5 subjects must fast 8 hours prior to the blood draw for hematology and chemistry laboratory tests. At Screening, and Month 12/Exit/Early termination visit, lipid may be obtained in the fasting or non-fasting state.

^g This is only applicable if the subject has consented to collection of blood for pharmacogenomics (approximately 10 mL of blood). This sample should be collected at the Day 14 visit, but may be collected at any time during the study or at a separate post study visit, if necessary.

^h Refer to Section 8.1.3 for assessments and requirements prior to randomization.

ⁱ After IP administration, slit-lamp biomicroscopy is performed first and then indirect ophthalmoscopy, in both eyes within 30 minutes of IP administration.

^j Intraocular pressure (IOP) is measured in both eyes at approximately 40 ± 10 minutes after IP administration. If IOP is increased ≥ 10 mmHg 40 ± 10 minutes after IP administration compared to prior to IP administration, administer topical IOP lowering medication for use until the subject returns for follow-up per the investigator's discretion. (An unscheduled visit may apply). IOP increase of ≥ 10 mmHg at any visit compare to the Baseline (Day 1) assessment should be reported as an AE.

^k Any required blood or urine sample is to be collected before injection of fluorescein.

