Verify that central laboratory results from blood and urine collected at screening have been obtained and reviewed.

Perform the following assessments prior to randomization and prior to administration of IP:

- If the subject is a woman of child-bearing potential, conduct urine pregnancy test. A positive pregnancy test requires exclusion from the study.
- Assess BCVA using ETDRS charts to confirm study eye(s) eligibility (inclusion Section 5.1, #5)
- Administer dilation eye drops (1% Mydriacyl and 2.5% phenylephrine or equivalent applied topically).
- Administer the VFQ-25.
- Obtain fundus photography for immediate submission to reading center.
- Measure IOP.
- Perform slit-lamp biomicroscopy. Assess intended study eye(s) eligibility with respect to VH score ($\geq 1.5+$ in each intended study eye).
- Perform indirect ophthalmoscopy.
- Perform OCT.
- Perform fluorescein angiography (recommended post investigator eligibility confirmation).

- Assess for adverse events.
- Record concomitant medications (including systemic corticosteroid medication status).

Confirm qualifying VH score for each of the subject's intended study eyes has been obtained from the Reading Center based on fundus photography at Day 1. Perform final review of inclusion/exclusion criteria. If the subject and the subject's intended study eye(s) meet all eligibility criteria, randomize the eye(s) into the study using the EDC system (Medidata, including IWRS component) to obtain the assigned vial number(s) to be dispensed to the study eye(s).

The unmasked investigator or designee performs IP preparation and administration as specified in Section 6.2.2 and Section 6.2.3.

Perform the following post IP administration assessments in both eyes:

- Within 30 minutes after the administration of IP:
 - Perform slit-lamp biomicroscopy
 - Perform indirect ophthalmoscopy
- Measure IOP as follows: At approximately 40 (±10) minutes following administration of IP, measure IOP by applanation tonometry. If there is an increase of ≥ 10 mmHg at 40 (±10) minutes post IP administration compared to prior to IP administration, administer topical IOP-lowering drops until the subject returns for follow-up, per the investigator's discretion. (An unscheduled visit may apply). Note that IOP increase of ≥ 10 mmHg should be reported as an adverse event.

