8.2.7. Intraocular Pressure

Intraocular Pressure (IOP) will be measured during screening and at each follow-up study visit. The examiner will measure IOP in each eye and record results in mmHg (e.g., 24). A single measurement is made to obtain a determination of IOP. The same contact tonometer employing the investigator's standard technique will be used throughout the study.

At visits when IP is administered, IOP will be measured prior to IP administration and at approximately 40 (\pm 10) minutes after IP administration. See the visit details of dosing visits (e.g., Day 1 visit details, Section 8.1.3).

Tonometer calibration: The tonometer must be calibrated for accuracy before the first subject undergoes screening, and periodically according to manufacturer's instructions thereafter, until the last subject has exited the study. For checking calibration, follow the manufacturer's instructions. If when checked, the variation is within ± 2 mmHg, the tonometer is considered adequately calibrated. However, if the variation exceeds this amount, the tonometer should be sent for repair and a different, adequately calibrated instrument should be used for IOP measurement. The date of each calibration, along with the name and signature (or initials) of the person who performed the calibration, must be documented. The tonometer calibration record will be retained as a part of the study record.

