8.2.13. Events of Special Interest

Events of Special Interest (ESIs) are medical events both anticipated and unanticipated that may have particular impact on the benefit/risk profile of DE-109 and therefore may require more detailed characterization. The DE-109 Investigational Brochure is the source for defining the DE-109 ESIs and should be consulted for further information.

The DE-109 ESIs are specific to the study eye only and are as follows:

- Clinically significant new or worsening of uveitis, defined as satisfaction of any of the following:
 - Worsening of uveitis in the study eye as indicated by at least a 2-step increase in VH score (i.e., 0 to ≥ 2+, 0.5+ to ≥ 3+, 1+ to ≥ 3+, 1.5+ to ≥ 4+, or 2+ to ≥ 4+) as compared to the baseline (Day 1) VH score or the best achieved VH score postbaseline.
 - Severe deterioration of vision in the study eye due to worsening of uveitis that is indicated by at least doubling of the visual angle (loss of 3 or more lines [≥15 ETDRS letters]) as compared to baseline (Day 1) BCVA.
 - New or worsening retinal or choroidal uveitic lesion(s) in the study eye as compared to baseline (Day 1).
 - New or worsening uveitis otherwise deemed clinically significant by the investigator in the study eye as compared to the baseline (Day 1).

Note: When documenting clinically significant new or worsening uveitis, the anatomic location (e.g., anterior uveitis, intermediate uveitis, posterior uveitis, or panuveitis) should be specified.

- Endophthalmitis / Sterile Endophthalmitis in the study eye A guided questionnaire is provided as part of the eCRFs to facilitate the documentation of endophthalmitis and sterile endophthalmitis. Endophthalmitis is also to be reported as an SAE (Section 10.4).
- Traumatic cataract in the study eye
- Vitreoretinal hemorrhage in the study eye
- Drug depot in visual axis in the study eye
- Retinal detachment (also to be reported as an SAE, Section 10.4) in the study eye
- Increased IOP (> 10 mmHg as compared to baseline). Note that certain instances of increased IOP are to be reported as an SAE (IOP >35 mmHg that persists for at least 7 days despite pharmacologic therapy, Section 10.4) in the study eye.
- Cataract (new or worsening from baseline) in the study eye
- Investigational product administration error considered to be significant by the investigator (examples include administration of IP from an incorrect kit and IP administration error attributed to some aspect of the instructions provided)

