8.3. Subgroup Analyses

The homogeneity of treatment effects among prospectively defined subgroups will be assessed via descriptive statistics of VH 0 response rate, including Mantel-Haenszel weighted rates and rate difference and it 95% CI, by the number of treated eyes for the following subgroups:

- Age (< 65 or \geq 65 years)
- Sex (males or females)
- Race (White or non-White)
- Country (US or non-US)
- Baseline VH score of the study eye (1.5+, 2+, or '3+ or 4+')
- Anatomic location of uveitis of study eye at baseline (intermediate, posterior, intermediate + posterior, or panuveitis)
- Intent-to-taper status at baseline (yes or no)
- Mean diurnal IOP at baseline ($< 25 \text{ or } \ge 25 \text{ mmHg}$)
- Baseline BCVA score of the study eye (≤ 70 letters or >70 letters)
- Baseline BCVA score of the study eye (≤ 65 letters or > 65 letters)
- Presence of macular edema in the study eye at baseline (yes [CST ≥ 300 microns] or no [CST < 300 microns])

Similarly, subgroup analyses will also be performed for the composite score. Other subgroup analyses may be performed as deemed necessary.

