9.3. Intraocular Pressure

IOP and change from baseline in IOP will be summarized by analysis visit.

Change after injection in IOP will be summarized by injection visit. Subjects with any increase of ≥ 10 mmHg in IOP after injection will be listed.

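### The SAP leaves reporting of raised IOP to discretion against the protocol's rule, has no threshold output for rises over Day 1, and names a diurnal IOP subgroup that cannot be computed

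*SAP*

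**What the plan says.** **AE reporting.** Protocol 1.3, footnote j: "IOP increase of ≥ 10 mmHg at any visit compare to the Baseline (Day 1) assessment should be reported as an AE". SAP 3.4 (Table 1, footnote j) carries the same sentence. The dosing-visit text in Protocol 8.1.3 (Day 1) and 8.1.6 (Month 2, applied to the other dosing visits) reads: "Note that IOP increase of ≥ 10 mmHg should be reported as an adverse event". That sentence names no reference value; it follows an instruction about post- versus pre-administration IOP. SAP 9.1.2, Table 3, says that "the elevated IOP, depending on the level of elevation, might be reported as an AE" at the investigator's discretion, with no threshold and no reference.

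**ESI.** Protocol 8.2.13 lists "Increased IOP (> 10 mmHg as compared to baseline", a strict inequality. SAP 9.1.1.5 repeats it.

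**Analysis.** SAP 9.3 summarises IOP and its change from baseline by analysis visit, and change after injection by injection visit. Its one threshold output is that subjects with a rise of at least 10 "mmHg in IOP after injection will be listed".

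**Subgroup.** SAP 8.3 includes "Mean diurnal IOP at baseline", cut at 25 mmHg. Protocol 8.2.7 says: "A single measurement is made to obtain a determination of IOP".

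**The concern.** Protocol 2.3 presents a minimal effect on IOP as part of the benefit/risk case, and SAP 2.3.4 names IOP as a safety endpoint. A reader of the study report will want to know how many eyes in each arm rose by a stated amount over baseline. Under the plan that count comes only from events that sites chose or were told to report, and the documents do not describe the reporting rule in one way. At injection visits the post-dose reading is taken by the unmasked investigator (Protocol 6.3), and masked and unmasked investigators both record AEs (Protocol 8.3). If discretion applied, it could therefore be exercised by someone who knows the arm. A count taken directly from the readings would not depend on any of this.

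Separately, a subgroup defined on a variable that nobody measures cannot be produced as specified. The programmer would have to choose a substitute that the SAP does not name.

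**Working it through.** No plan figure needs reproducing here, so the check sets the rules side by side and applies them to example readings.

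**Step 1: the rules.**

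| Place | Class | Threshold (mmHg) | Reference | Visits | Obligation |
|---|---|---|---|---|---|
| Protocol 1.3 and SAP 3.4, footnote j | AE | ≥10 | Day 1 | any | to be reported |
| Protocol 8.1.3, 8.1.6 | AE | ≥10 | none named | dosing visits | to be reported |
| SAP 9.1.2, Table 3 | AE | none | none | none | investigator's discretion |
| Protocol 8.2.13, SAP 9.1.1.5 | ESI | >10 | baseline | not limited | within 24 hours |
| SAP 9.3 | listing | ≥10 | same-visit pre-dose | injection visits | not applicable |

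There are three AE wordings and one separate ESI definition. The plain contradiction is between rows 1 and 3, and the SAP contains both.

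**Step 2: example readings** (illustrative, whole mmHg; the rise over Day 1 uses the higher of the visit's two readings).

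| Day 1 | Visit pre | Visit post | Rise over Day 1 | Post − pre | Footnote j AE | ESI | SAP 9.3 listing |
|---|---|---|---|---|---|---|---|
| 15 | 15 | 25 | 25−15 = 10 | 25−15 = 10 | yes | no | yes |
| 15 | 24 | 26 | 26−15 = 11 | 26−24 = 2 | yes | yes | no |
| 14 | 18 | 27 | 27−14 = 13 | 27−18 = 9 | yes | yes | no |
| 25 | 14 | 24 | 24−25 = −1 | 24−14 = 10 | no | no | yes |

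The listing and the Day 1 rules pick out different eyes. In the third row the pre-dose reading alone gives 18−14 = 4, so the result also depends on which reading feeds change from baseline at an injection visit. SAP 9.3 does not say. At a non-injection visit, a Day 1 value of 14 and a Month 5 value of 24 give exactly +10: an AE by footnote j, not an ESI, and outside the listing.

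**Step 3: coverage.** In the double-masked period the after-injection listing draws on Day 1, Month 2 and Month 4. IOP is also measured at Day 14 and Months 1, 3 and 5, where no threshold output exists. By contrast, SAP 9.4, 9.4.1 and 9.5 list worsening from baseline for graded biomicroscopy findings and cataract severity (2 units or more) and for cup/disc ratio (0.2 or more).

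**Step 4: does ≥10 versus >10 matter?** The documents give no IOP distribution. Assume the change over Day 1 is normal with mean μ from 0 to 2 and SD σ from 3 to 6 mmHg, recorded in whole mmHg. Then P(≥10) = 1 − Φ((9.5−μ)/σ) and P(>10) = 1 − Φ((10.5−μ)/σ).
- μ = 0, σ = 3: 0.077% and 0.023%; share exactly 10 = (0.077−0.023)/0.077 ≈ 70%.
- μ = 2, σ = 6: 10.56% and 7.83%; share exactly 10 = (10.56−7.83)/10.56 ≈ 26%.

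So between about a quarter and 70% of the readings meeting ≥10 would fall outside >10. This needs whole-number recording. Protocol 8.2.7 gives 24 as its example; SAP Table 3 says one decimal place, 24.0. With real decimals, exact ties would be rarer.

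**Step 5: the diurnal subgroup.** Day 1 provides one pre-dose reading and one about 40 minutes after administration (Protocol 8.2.7). A diurnal mean needs several pre-treatment readings across a day. None is scheduled, and the SAP does not define the term.

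**The case against.** Much can be said for the plan. SAP 9.3 does summarise rises over Day 1 from the readings. SAP 5 sets the statistics to include the maximum, so the largest rise appears for each arm and visit, and it also provides for listing individual data with derived variables. A reader might infer that rises over baseline are not analysed at all; that is wrong. Only the threshold count or listing is missing, and Protocol 9.5.4 asks for no more than descriptive summaries.

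A reader might also count four conflicting AE triggers. The ESI definition is a separate reporting class for study eyes and may properly carry its own cut-off, so a rise of exactly 10 that is an AE but not an ESI is not in itself a contradiction. Nor does the dosing-visit text clearly contradict footnote j. It names no reference, footnote j follows the same order of sentences, and on Day 1 the two references coincide. The wording is unclear at later dosing visits, no more than that.

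It is tempting to say that the ≥25 mmHg stratum would be nearly empty. Exclusion 9 covers uncontrolled glaucoma above 21 mmHg on medical therapy and sets no ceiling for other subjects, so the documents do not show this.

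Finally, sites report under the protocol, not under a note in a SAP table, which limits the practical harm of the discretion wording. That stands and is why the point is minor. What survives is the SAP's disagreement with itself, the absent threshold output and the unmeasured subgroup variable.

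**Conclusion.** The point holds in three limited parts. The discretion wording in SAP Table 3 contradicts the reporting rule in footnote j, which the SAP itself repeats; the unreferenced dosing-visit note and the differing ESI inequality add uncertainty, part of it within the protocol alone. SAP 9.3 gives no table or listing that identifies from the readings the eyes crossing 10 mmHg over Day 1. The diurnal subgroup cannot be computed for any subject from the scheduled measurements.

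Severity is minor. The primary efficacy test and the sample size are untouched, and the subgroup is one of eleven descriptive ones. The three findings rest on the text alone. The 26% to 70% range rests on the assumed distribution and on whole-mmHg recording, which the two documents describe differently. No view is taken on which IOP threshold is right.

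**What to change.** 1. Reconcile the AE wording in Protocol 1.3 and SAP 3.4 (footnote j), Protocol 8.1.3 and 8.1.6, and SAP Table 3, stating the reference value and the visits covered. Confirm whether the difference between ≥10 for AEs and >10 for ESIs is intended. Reconcile the recording precision in Protocol 8.2.7 and SAP Table 3.
2. In SAP 9.3 add, by arm and visit and for any double-masked visit, the number of study eyes with measured rises of ≥10 and of >10 mmHg over Day 1, stating which reading is used at injection visits. Give the same counts for post- versus pre-administration change. Showing both cut-offs avoids having to choose between them.
3. In SAP 8.3 replace the diurnal mean with the study eye's Day 1 pre-dose IOP, with the cut-point fixed before unmasking, or delete the subgroup.

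The cost is SAP wording, one table from data already collected and a short clarification to sites. No new measurement is needed.
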